11.0 STATISTICAL METHODS

11.1 Statistical Plan

A Statistical Analysis Plan (SAP), detailing the intended statistical analyses of the study data, will be prepared as a separate document and finalized before database lock. Any deviation from the original SAP will be described and justified in the final report, as appropriate. The procedure for accounting for missing, unused and spurious data will be included in the SAP.

All statistical analyses will be performed by [REDACTED] and conducted using the Statistical Analysis System (SAS®), Version 9.4 or higher. [REDACTED]

11.2 Determination of Sample Size

For the primary endpoint analysis (proportion of patients in the PP population that are identified as Responders at the end of the treatment period evaluated on Day 8 or Day 9), sample size is estimated for therapeutic equivalence of the Test to the Reference product and superiority of each of the active treatments groups over Placebo.

CONFIDENTIAL PROTOCOL

A Randomized, Double-Blind, Placebo-Controlled, Parallel-Design, Multiple-Site Study to Evaluate the Therapeutic Equivalence of Estradiol Vaginal Cream, USP, 0.01% (Prasco LLC) to Estrace[®] Cream (Estradiol Vaginal Cream, USP, 0.01%) (Warner Chilcott) in the Treatment of Vulvar and Vaginal Atrophy, 71759501

[REDACTED]

[REDACTED]

[REDACTED]

11.3 Study Populations

11.3.1 Per-Protocol Population

The PP population will include all randomized patients who:

- Met the inclusion/exclusion criteria as defined in this protocol at Visit 1 and 2.
- Did not have any significant protocol deviations.
- Did not develop any concurrent vaginal infection or illness exhibiting symptoms similar to VVA, or symptoms that in the Investigator's opinion would interfere with primary and secondary endpoint assessments.
- Completed the last study visit (Visit 3) within window (Day 8 or Day 9).
- Were compliant with dosing between 75%-125% of the required doses.

Any patient who withdraws from the study because of lack of efficacy will be included in the PP population as a Non-Responder, provided they did not have any significant protocol deviations that would affect treatment evaluation.

11.3.2 Modified Intent-to-Treat Population

The modified Intent-to-Treat (mITT) population will include all randomized patients who:

- Administered at least one dose of randomized study product.
- Had a post-randomization evaluation.

CONFIDENTIAL PROTOCOL

A Randomized, Double-Blind, Placebo-Controlled, Parallel-Design, Multiple-Site Study to Evaluate the Therapeutic Equivalence of Estradiol Vaginal Cream, USP, 0.01% (Prasco LLC) to Estrace[®] Cream (Estradiol Vaginal Cream, USP, 0.01%) (Warner Chilcott) in the Treatment of Vulvar and Vaginal Atrophy, 71759501

11.3.3 Safety Population

The safety population will include all patients who are randomized and received study product.

11.4 Baseline Comparability

Baseline comparability of all treatment groups will be evaluated separately in the PP, mITT and Safety populations. The following baseline demographics (determined from their initial study visit) will be evaluated:

- Age (years)
- Gender (male/female)
- Ethnicity (Hispanic/non-Hispanic)
- Race (White, Black/African American, Native Hawaiian or Other Pacific Islander, Asian, American Indian or Alaska Native, Other)
- Natural or surgical menopause
- Duration of postmenopausal status
- Baseline signs and symptoms
- Baseline % of the three major vaginal wall cell types (basal/parabasal cells, intermediate cells and superficial cells)
- Vaginal pH

Summary tables by treatment group will be presented. Continuous variables will be summarized using descriptive statistics (number of observations, median, minimum, maximum, mean and standard deviation). Categorical variables will be summarized using frequencies and percentage. Baseline treatment comparisons will be presented using Chi-Square or Cochran-Mantel-Haenszel (CMH) tests for the categorical variables, and Analysis of Variance (ANOVA) for the continuous variables.

All data will be listed by treatment and patient.

11.5 Efficacy Endpoints

Primary Efficacy Endpoint

The primary efficacy endpoint is the proportion of patients in each treatment group that are identified as Responders at the end of the treatment period evaluated on Day 8 or Day 9.

A “Responder” is defined as a patient with at least a 25% reduction from baseline in the sum of % basal/parabasal + % intermediate cells on vaginal cytology AND vaginal pH < 5.0 with a change from baseline vaginal pH of at least 0.5.

Secondary Efficacy Endpoint

The secondary efficacy endpoint is the proportion of patients in each treatment group that are considered a Treatment Success at the end of the treatment period evaluated on Day 8 or Day 9.

CONFIDENTIAL PROTOCOL

A Randomized, Double-Blind, Placebo-Controlled, Parallel-Design, Multiple-Site Study to Evaluate the Therapeutic Equivalence of Estradiol Vaginal Cream, USP, 0.01% (Prasco LLC) to Estrace[®] Cream (Estradiol Vaginal Cream, USP, 0.01%) (Warner Chilcott) in the Treatment of Vulvar and Vaginal Atrophy, 71759501

A “Treatment Success” is defined as a score of 0 or 1 on Day 8 or Day 9 for the symptom identified at baseline as the most bothersome. This evaluation will be based on (one) patient self-assessed symptom of VVA (vaginal dryness, vaginal and/or vulvar irritation/itching, dysuria, or vaginal pain associated with sexual activity) on a scale of 0 to 3 where 0 = none and 3 = severe. Evaluation of vaginal bleeding during sexual activity will be based on a Score of 1 (presence) if it is identified by the patient as the most bothersome symptom at baseline and a score of 0 (absent) on Day 8 or Day 9. Refer to Appendix B for rating scales.

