10.3 Selection of Study Population

10.3.1 Inclusion Criteria

1. Signed IRB-approved ICF that meets all criteria of current FDA regulations.
2. Postmenopausal females aged 30-75 years inclusive. Postmenopausal is defined as follows:
 - a. At least 6 months of spontaneous amenorrhea.
 - b. At least 6 weeks post-surgical bilateral oophorectomy, with or without hysterectomy.
 - c. Hysterectomy without oophorectomy if of age that the Investigator believes would have naturally reached 12 months of spontaneous amenorrhea if uterus had remained intact.
3. Patients with a serum Follicle Stimulating Hormone (FSH) level of ≥ 40 mIU/mL at Screening.
4. Have $\leq 5\%$ superficial cells on vaginal smear cytology.
5. Have a vaginal pH > 5.0 .
6. At least one of the following patient self-assessed moderate to severe symptoms of VVA from the following list that is identified by the patient as being most bothersome to her:

CONFIDENTIAL PROTOCOL

A Randomized, Double-Blind, Placebo-Controlled, Parallel-Design, Multiple-Site Study to Evaluate the Therapeutic Equivalence of Estradiol Vaginal Cream, USP, 0.01% (Prasco LLC) to Estrace[®] Cream (Estradiol Vaginal Cream, USP, 0.01%) (Warner Chilcott) in the Treatment of Vulvar and Vaginal Atrophy, 71759501

- Vaginal Dryness
- Vaginal and/or Vulvar Irritation/Itching
- Dysuria
- Vaginal Pain associated with sexual activity
- Vaginal Bleeding associated with sexual activity (presence or absence)

*Provided that patient is currently sexually active and plans to remain so throughout study.

7. Have “Normal” Screening mammogram completed within 9 months before Screening in all patients > 40 years old, with no findings that, in the opinion of the Investigator, would indicate any suspicion of breast malignancy.
8. Normal clinical breast examination at Screening.
9. Patients with an intact uterus (including patients who underwent a partial hysterectomy) must have a documented papanicolaou (PAP) smear conducted within the previous 12 months with no findings that the Investigator believes would contraindicate the use of topical vaginal estradiol.
10. Patients with an intact uterus should have vaginal ultrasonography results within 3 months before Screening to confirm an inactive endometrial lining, defined as endometrial thickness < 4 mm.

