10.3.3 Restrictions During the Study

Patients will be instructed to refrain from the following throughout the study:

- Any kind of estrogen, progesterone or androgen hormone replacement.
- Any other treatments, prescription, OTC or natural products or natural methods, for the treatment of vaginal dryness/irritation including but not limited to vaginal lubricants, oils, creams, jellies, food products or saliva.
- Any vaginal drug products other than the study product (e.g., vaginal anti-fungals).
- Use within 30 days of Screening with known strong CYP3A4 inducers or inhibitors that, in the opinion if the Investigator, may affect estrogen metabolism. Examples of strong CYP3A4 inhibitors are macrolide antibiotics such as clarithromycin and telithromycin; azole antifungals such as itraconazole and ketoconazole; antidepressants such as nefazodone; and foods such as grapefruit or grapefruit juice. Examples of strong CYP3A4 inducers are anticonvulsants such carbamazepine and phenytoin; bactericidals such as rifampin and rifabutin; and natural health products such as St John's wort.

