10.6.14 Provide Patient Diary

At Visits 1 and 2, patients will be provided with a diary to record other concomitant medications and AEs. The patients will also receive on-site training on completing the diary. Date and time of dosing should be recorded in the diary dispensed at Visit 2.

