14.2 APPENDIX B: Definitions and Severity ratings for Signs and Symptoms

Vaginal Dryness		
Score	Severity	Description
0	None	No noticeable lack of vaginal lubrication or secretions reported or observed
1	Mild	Episodic loss of lubrication/secretions or noticed some reduction in general secretions, does not interfere with daily activities
2	Moderate	Symptom present most of the time, and noticeable but overall is tolerable and does not interfere with daily activities
3	Severe	Very minimal or no natural vaginal lubrication/secretions almost all of the time and interferes with normal activities

Vaginal/Vulvar Irritation/Itching		
Score	Severity	Description
0	None	No irritation or itching reported.
1	Mild	Occasional irritation/itching but does not interfere with daily activities
2	Moderate	Frequent irritation/itching that can be uncomfortable but generally does not interfere with daily activities
3	Severe	Very frequent or continuous irritation/itching of the vaginal area, may interfere with daily activities.

Dysuria		
Pain or discomfort during urination		
Score	Severity	Description
0	None	No pain or discomfort during urination reported.
1	Mild	Occasional or slight discomfort during urination but tolerable
2	Moderate	Some discomfort during urination at least 50% of the time which can be painful but overall tolerable.
3	Severe	Urination nearly always painful, usually intolerable and causing disruption to daily activities

CONFIDENTIAL PROTOCOL

A Randomized, Double-Blind, Placebo-Controlled, Parallel-Design, Multiple-Site Study to Evaluate the Therapeutic Equivalence of Estradiol Vaginal Cream, USP, 0.01% (Prasco LLC) to Estrace[®] Cream (Estradiol Vaginal Cream, USP, 0.01%) (Warner Chilcott) in the Treatment of Vulvar and Vaginal Atrophy, 71759501

Vaginal Pain during Sexual Activity		
Suffers discomfort or pain during sexual activity that may be restrictive.		
Score	Severity	Description
0	None	No discomfort or pain
1	Mild	Some feeling of vaginal soreness or pain, during or after sexual activity. Does restrict frequency of or type of sexual activity.
2	Moderate	Vaginal pain during sexual activity such that frequency and type of sexual activity have been disrupted. Lubrication may be needed for penetration
3	Severe	Vaginal penetration very painful and impossible without vaginal lubrication. Discomfort such that frequency of sexual activity significantly reduced.

Vaginal bleeding during or after sexual activity		

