At each visit each patient must also clearly identify which is the most bothersome sign/symptom to her, even if she rates two or more symptoms the same severity rating.		
Score	Severity	Description
0	Absent	No vaginal bleeding observed
1	Present	Bleeding observed during or soon after vaginal activity

CONFIDENTIAL PROTOCOL

A Randomized, Double-Blind, Placebo-Controlled, Parallel-Design, Multiple-Site Study to Evaluate the Therapeutic Equivalence of Estradiol Vaginal Cream, USP, 0.01% (Prasco LLC) to Estrace[®] Cream (Estradiol Vaginal Cream, USP, 0.01%) (Warner Chilcott) in the Treatment of Vulvar and Vaginal Atrophy, 71759501

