### Secondary Efficacy Endpoint

The secondary efficacy endpoint is the proportion of patients in each treatment group that are considered a Treatment Success at the end of the treatment period evaluated on Day 8 or Day 9.

A “Treatment Success” is defined as a score of 0 or 1 on Day 8 or Day 9 for the symptom identified at baseline as the most bothersome. This evaluation will be based on (one) patient self-assessed symptom of VVA (vaginal dryness, vaginal and/or vulvar irritation/itching, dysuria, or vaginal pain associated with sexual activity) on a scale of 0 to 3 where 0 = none and 3 = severe. Evaluation of vaginal bleeding during sexual activity will be based on a Score of 1 (presence) if it is identified by the patient as the most bothersome symptom at baseline and a score of 0 (absent) on Day 8 or Day 9.

Baseline is defined as the symptom score at Randomization Visit 2.

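### The secondary endpoint has no rule for a woman with no sexual activity in the treatment week: bleeding then scores as Treatment Success by default, and pain has no defined score

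*Protocol*

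**What the plan says.** The general rule for success in Protocol 11.5 "is defined as a score of 0 or 1 on Day 8 or Day 9 for the symptom identified at baseline as the most bothersome". Bleeding has its own rule, present at baseline and absent at the end: Protocol 11.5 asks that it be her most "bothersome symptom at baseline and a score of 0 (absent) on Day 8 or Day 9". SAP 7 repeats this, requiring that bleeding be identified "as the most bothersome symptom at baseline and a score of 0 (absent) on Day 8 or Day 9".

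The scales are in Protocol Appendix B and SAP Appendix A. Bleeding score 0 reads "No vaginal bleeding observed". Pain score 0 is the absence of pain or discomfort. Neither scale has a level for no activity, and neither states a recall period.

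The entry criteria (Protocol 10.3.1, item 6) carry a footnote: "Provided that patient is currently sexually active and plans to remain so throughout study". This is an intention at entry. On data collection, Protocol 10.6.14 says: "At Visits 1 and 2, patients will be provided with a diary to record other concomitant medications and AEs". Dosing times are added to the diary given at Visit 2. The Visit 3 list in 10.5.3 has the symptom ratings but no question on whether activity took place. SAP 8.5 applies LOCF to early discontinuation and is silent on a symptom that could not be assessed.

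Protocol 10.3.3 bars treatments for dryness or irritation throughout the study, "including but not limited to vaginal lubricants, oils, creams, jellies, food products or saliva".

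**The concern.** A symptom that occurs only during an activity cannot be judged if the activity did not occur. With seven days of treatment and assessment on Day 8 or 9, some women may have no activity in the interval. If they are credited with success, or given a score that does not depend on treatment, they add the same amount to every arm. This dilutes both comparisons planned for the endpoint: Test minus Reference is pulled toward zero, which is the non-conservative direction for equivalence, and the active-placebo difference shrinks. The endpoint is supportive, but it is the trial's only patient-reported efficacy endpoint and has its own formal equivalence and superiority tests (SAP 8.2.2). If activity is not recorded, the affected women cannot be identified afterwards.

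**Working it through.** **1. Apply the rules to a woman with no activity between Visit 2 and Visit 3.**

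- *Bleeding as most bothersome symptom.* She was scored present at Visit 2. No bleeding has been seen since, so she fits score 0 and is a Treatment Success. The definition gives this result directly.
- *Pain as most bothersome symptom.* Score 0 fits, because she had no pain. Score 1 as printed speaks of restricted activity. Score 2 speaks of disrupted activity. Score 3 speaks of markedly less frequent activity and "Vaginal penetration very painful and impossible without vaginal lubrication". Success is 0 or 1 and failure is 2 or 3, so she can be placed on either side of the cut. If the restriction wording in score 1 is a slip, scores 0, 2 and 3 still span the cut.

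**2. Effect on the comparisons.** The plan gives no figure for this, and the sample-size inputs are blacked out, so there is nothing to reproduce. Let p be the success rate among assessable women in an arm, q the share scored without regard to treatment, and c the fraction of those scored as success. Take q and c as equal across arms. Then

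observed rate = (1-q)p + qc

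difference between arms = (1-q)(p₁ - p₂)

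The term qc cancels. The value of c moves the rates up or down but does not alter the shrinkage.

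**3. Size, on assumed inputs.** Let f be the share of women whose most bothersome symptom is tied to sexual activity, and g the share of those who are inactive and scored without regard to treatment. Then q = f × g. With f from 10% to 50% and g from 20% to 60%:

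- lowest q = 0.10 × 0.20 = 0.02, so a true 20-point difference appears as 0.98 × 20 = 19.6 points;
- highest q = 0.50 × 0.60 = 0.30, so it appears as 0.70 × 20 = 14.0 points.

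For the placebo contrast, 535 women at 2:2:1 give 535 × 2/5 = 214 per active arm and 535/5 = 107 on Placebo. The table assumes success rates of 60% active and 40% Placebo, all inactive women scored as success (c = 1), a two-sided 0.05 test, no site strata and no exclusions.

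| q | Active | Placebo | Difference | Power |
|---|---|---|---|---|
| 0 | 60.0% | 40.0% | 20.0 | 92.7% |
| 0.02 | 60.8% | 41.2% | 19.6 | 91.7% |
| 0.12 | 64.8% | 47.2% | 17.6 | 85.6% |
| 0.30 | 72.0% | 58.0% | 14.0 | 70.9% |

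With 70% against 50%, power falls from 93.7% (q = 0) to 93.0%, 88.3% and 76.3% at the same three values of q.

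**4. Does scoring inactive women as failures cure it?** Take assumed rates of 50% active and 30% Placebo.

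| q | Scored as success (c = 1) | Scored as failure (c = 0) | Difference, either way |
|---|---|---|---|
| 0.10 | 55% vs 37% | 45% vs 27% | 18 |
| 0.20 | 60% vs 44% | 40% vs 24% | 16 |

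Failure scoring removes the false credit but not the attenuation.

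**5. Lubrication.** Pain must be moderate or severe to qualify (Protocol 10.6.6). The Moderate anchor says lubrication may be needed, the Severe anchor says penetration is impossible without it, 10.3.3 bars lubricants, and the entry footnote expects continued activity. Protocol 10.3.4 lists use of restricted medication as non-compliance, and 11.3.1 removes significant deviations from PP. These passages are in tension.

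**The case against.** A reader might infer more than the documents support.

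- *That inactivity counts as success for pain too.* No text says so. A woman who abstains because of pain fits score 2 or 3 at least as well as 0, and if she is scored that way her score does reflect her condition. Protocol 10.6.6 has blinded staff or the Investigator question her, which may resolve some cases. For pain, the supportable statement is that the score is undefined.
- *That the effect is concentrated in the most severely affected.* Only pain has a severe level; bleeding is present or absent. For severe pain the anchors point toward failure as readily as success.
- *That the lubricant restriction makes inactivity likely, or compliance impossible.* No rate of inactivity is given, sexual activity is not defined as penetration, the anchor describes the woman's state when rated, and entry requires current activity with an intention to continue. The tension in wording is real; impossibility is not shown.
- *That the trial's conclusions are at risk.* Equivalence and superiority are each declared on the primary endpoint alone (Protocol 11.6), and SAP 8.2.2 calls the secondary equivalence test supportive.

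The CRF booklet named in the SAP introduction is not available and the table shells are blacked out, so an activity item could exist there. That limits the finding to the readable text. It does not supply the missing scoring rule in the protocol or SAP. The bleeding result and the gap for pain both stand.

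**Conclusion.** The concern holds as a gap in the secondary endpoint's definition. For bleeding, the written rule makes an inactive woman a Treatment Success regardless of treatment. For pain, her score is undefined and may fall on either side of the cut. The consequence is shrinkage of every between-arm difference by (1-q), which needs q and c to be equal across arms and applies only to women scored without regard to treatment. The documents do not give q; on an assumed 2% to 30%, a 20-point difference becomes 19.6 to 14 points. If only bleeding patients are affected, q is bounded by the share naming bleeding, which is also not given. The change is worth making because it is cheap and cannot be reconstructed later, but it bears on a supportive endpoint only.

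**What to change.** 1. Add one yes/no item at Visit 3: sexual activity since the first dose.
2. State in Protocol 11.5 and SAP 7 and 8.5 that pain and bleeding scores are assessable only if the answer is yes.
3. In the PP secondary equivalence analysis, use assessable women.
4. In mITT, count non-assessable women as non-success, stating that LOCF from Visit 2 extends to this case. Protocol 10.6.6 requires a qualifying score at Visit 2, so the carried value is a non-success, provided that the bleeding-specific rule is applied. SAP 8.2.2 repeats only the 0-or-1 rule, under which a carried bleeding score of 1 would count as success; it should be aligned with SAP 7.
5. Add a supportive mITT analysis that excludes non-assessable women, since step 4 does not remove the attenuation.
6. Report non-assessable counts by arm.
7. Separately, reconcile the entry footnote on continued activity, the lubricant restriction in 10.3.3, and the Moderate and Severe pain anchors.

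The cost is one CRF question and a few sentences in each document. There will be somewhat fewer evaluable women. Exclusion also conditions on behaviour after randomization that treatment may influence; for example, it drops women who abstain because pain persists. That is why both the non-success and the exclusion analyses are needed.

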11.6 Efficacy Analyses

Primary Endpoint Analysis

Therapeutic Equivalence:

Therapeutic equivalence will be evaluated for both primary and secondary endpoints in the PP population. If the 90% confidence interval (calculated using Yates’ continuity correction) on the absolute difference between the proportion of patients identified as Responders in the Test and Reference groups ($p_T - p_R$) is contained within the range [-20%, +20%] then therapeutic equivalence of the Test product to the Reference product will be considered to have been demonstrated.

The same statistical approach will be conducted for analysis of the secondary endpoint in the PP population.

To declare therapeutic equivalence of the Test product to the Reference product, equivalence must be demonstrated for only the primary endpoints in the PP population.

Superiority to Placebo

Superiority of the Test and Reference products against the Placebo product for the primary endpoint will be evaluated in the mITT population using last observation carried forward (LOCF). If the proportion of Responders in the Test and the Reference product groups is numerically and statistically superior to that of the Placebo ($p < 0.05$; using a two-sided CMH test, stratified by clinical site) then superiority of the Test and Reference products over Placebo will be concluded.

The same statistical approach will be conducted for analysis of the secondary endpoint in the mITT population.

To declare superiority of the Test and Reference products over Placebo, their superiority must be demonstrated for only the primary endpoint in the mITT population.

Treatment-by-Site Interaction and Pooling of Clinical Sites

As this is a multiple-site study, the interaction of treatment-by-site may be evaluated for the primary efficacy endpoint in the PP population for equivalence testing. The treatment-by-site interaction will be evaluated by the Breslow-Day test for homogeneity of the odds ratio at the 5% significance level ($p < 0.05$, 2-sided). A site(s) with a low enrollment rate(s) may be pooled with its geographically closest site, so as to avoid bias in the stratification of the sites in the CMH test and in the estimation of a treatment-by-site interaction effect. The pooling will be done for low enrolling sites that account for less than 4-7% of the total number of patients in the PP population at the site with the highest

CONFIDENTIAL PROTOCOL

A Randomized, Double-Blind, Placebo-Controlled, Parallel-Design, Multiple-Site Study to Evaluate the Therapeutic Equivalence of Estradiol Vaginal Cream, USP, 0.01% (Prasco LLC) to Estrace[®] Cream (Estradiol Vaginal Cream, USP, 0.01%) (Warner Chilcott) in the Treatment of Vulvar and Vaginal Atrophy, 71759501

enrolling rate in the PP population. If the treatment-by-site interaction term is found to be statistically significant ($p < 0.05$) for the primary endpoint, then the interaction term will also be assessed for clinical relevance before pooling the data across sites. This will include examination of “Responder” rates at each site where sample sizes per treatment may be influential in the assessment of the interaction

